10.8 Unscheduled Additional Visit as needed

1. Clinical evaluation for symptoms to include physical exam and ECG as needed.
2. Obtain blood samples for evaluation: Complete blood count with differential, comprehensive metabolic panel, tacrolimus / sirolimus level, C-reactive protein, erythrocyte sedimentation rate (ESR), total immunoglobulins (IgG, IgA, IgM), anti-RBD, anti-spike and neutralizing antibody levels, PBMCs collected for cellular response assays including flow cytometry with intracellular staining, whole blood collected for cellular response assays, troponin / CK, cytokines, PT, PTT, INR (16 mL of venous blood).
3. AEs (solicited and unsolicited), SAEs, AESIs and MAAEs will be reviewed. Based on the information collected, participants may be asked to return to the clinic for evaluation.

11 ADVERSE EXPERIENCE REPORTING AND DOCUMENTATION

11.1 Adverse Events

An adverse event (AE) is any untoward medical occurrence in a clinical investigation of a participant administered a pharmaceutical product and that does not necessarily have a causal relationship with the treatment. An AE is therefore any unfavorable and unintended sign (including an abnormal laboratory

finding), symptom or disease temporally associated with the administration of an investigational product, whether or not related to that investigational product. Any medical condition that is present at the time that the subject is screened will be considered as baseline and not reported as an AE. However, if the severity of any pre-existing medical condition increases, it will be recorded as an AE.

AEs can be further divided into solicited AEs and unsolicited AEs. Solicited AEs are those for which the study team will specifically query the subject whether they occurred. Unsolicited AEs are those events that the subject report occurring without being queried about the specific event.

A suspected adverse event is one for which there is a ‘reasonable possibility’ that the drug caused the adverse event. A ‘reasonable possibility’ means there is evidence to suggest a causal relationship between the drug and the adverse event, but implies a lesser degree of certainty about causality compared with an adverse event. An unexpected AE is one of a type not identified in nature, severity, or frequency in the current Investigator’s Brochure or of greater severity or frequency than expected based on the information in the Investigator’s Brochure. All AEs will be assessed for severity and relationship to study intervention (Tables 3 and 4). Suspected, Unexpected, Serious Adverse Reactions (SUSAR) is an adverse event where a causal relationship with the study drug is at least possible but not listed in the Investigator Brochure (IB), Package Insert, and/or Summary of Product Characteristics and includes any of the following: suspected AE, unexpected AE and serious adverse experience (SAE). Episodes of myocarditis or pericarditis occurring in temporal association with vaccination will be reported as a SUSAR. Medically attended adverse event (MAAE) is defined as hospitalization, an emergency room visit or an otherwise unscheduled visit to or from medical personnel for any reason.

Frequency and grade of each solicited AE (local and systemic reactogenicity) will be collected until Day 7 using the FDA Toxicity Grading Scale to be recorded on a daily diary. Frequency and grade of each unsolicited AEs will be collected until Day 30. Frequency of any SAEs, AESIs and MAAEs will be collected until Day 180. After Day 30 through the end of study on Day 180, only SAEs, AESIs and MAAEs will be reported as AEs. All AEs, solicited and unsolicited, will be captured on the appropriate CRF. Information to be collected for AEs includes event description, date of onset, assessment of severity, relationship to study product and alternate possible etiology, date of resolution, seriousness, and outcome. AEs occurring during the study-collection and reporting period will be documented appropriately regardless of relationship. AEs will be followed to resolution or stabilization.

Solicited Adverse Events:

Solicited AEs are anticipated local and systemic AEs for which consistent collection of information is desired. Study clinicians will follow and collect resolution information for any reactogenicity symptoms that are not resolved within 7 days. Solicited AEs (i.e., reactogenicity) will be collected using a daily diary and recorded on the appropriate CRF from the time of the vaccination until 7 days post vaccination (Days 1-7). For this study, solicited AEs will be defined and graded as follows (Tables 3):

Table 3: Solicited Adverse Reactions and Grading

Phase I/II, Open-label Dose-finding Trial of High-Dose mRNA-1273 Booster for Lung Transplant Recipients
Confidential

Reaction	Grade 0	Grade 1	Grade 2	Grade 3	Grade 4
Injection site pain	None	Does not interfere with activity	Repeated use of over-the-counter pain reliever > (greater than) 24 hours or interferes with activity	Any use of prescription pain reliever or prevents daily activity	Requires emergency room visit or hospitalization
Injection site erythema (redness)	< (less than) 25 mm or < 2.5 cm	25 - 50 mm or 2.5 - 5 cm	51 - 100 mm or 5.1 - 10 cm	> 100 mm or > 10 cm	Necrosis or exfoliative dermatitis (severe skin rash causing skin discoloration or peeling)
Injection site swelling/induration (hardness)	< 25 mm or < 2.5 cm	25 - 50 mm or 2.5 - 5 cm	51 - 100 mm or 5.1 - 10 cm	> 100 mm or > 10 cm	Necrosis (severe swelling with skin discoloration, blistering, or peeling)
Axillary (underarm) swelling or tenderness ipsilateral to the side of injection	None	No interference with activity	Repeated use of over-the-counter (non-narcotic) pain reliever > 24 hours or some interference with activity	Any use of prescription (narcotic) pain reliever or prevents daily activity	Requires emergency room visit or hospitalization
Headache	None	No interference with activity	Repeated use of over-the-counter pain reliever > 24 hours or some interference with activity	Significant; any use of prescription pain reliever or prevents daily activity	Requires emergency room visit or hospitalization
Fatigue	None	No interference with activity	Some interference with activity	Significant; prevents daily activity	Requires emergency room visit or

Phase I/II, Open-label Dose-finding Trial of High-Dose mRNA-1273 Booster for Lung Transplant Recipients
Confidential

Reaction	Grade 0	Grade 1	Grade 2	Grade 3	Grade 4
					hospitalization
Myalgia (muscle aches all over body)	None	No interference with activity	Some interference with activity	Significant; prevents daily activity	Requires emergency room visit or hospitalization
Arthralgia (joint aches in several joints)	None	No interference with activity	Some interference with activity	Significant; prevents daily activity	Requires emergency room visit or hospitalization
Nausea/vomiting	None	No interference with activity or 1-2 episodes/24 hours	Some interference with activity or > 2 episodes/24 hours	Prevents daily activity, requires outpatient intravenous hydration (fluids given through blood veins)	Requires emergency room visit or hospitalization for low blood pressure
Chills	None	No interference with activity	Some interference with activity not requiring medical intervention	Prevents daily activity and requires medical intervention	Requires emergency room visit or hospitalization
Fever	< 38.0°C < 100.4°F	38.0 – 38.4°C 100.4 – 101.1°F	38.5 – 38.9°C 101.2 – 102.0°F	39.0 – 40.0°C 102.1 – 104.0°F	> 40.0°C > 104.0°F
Rash	No rash	Localized rash, without associated symptoms	Maculopapular rash (bumpy and red rash) covering < 50% body surface area	Generalized urticarial rash (hives or itchy rash) covering > 50% body surface area	Generalized exfoliative, ulcerative or bullous dermatitis (severe skin rash causing skin discoloration, peeling or blistering)

Reaction	Grade 0	Grade 1	Grade 2	Grade 3	Grade 4
If you experience any grade 4 symptom from your daily diary, or any other severe symptoms that prevents your daily activity AND requires you to see a doctor, please call [name] immediately at [contact]. The operator will answer the call, please tell them that you would like to "page [name]". [name] or another covering Dr will call you back.					

Source: Guidance for industry – Toxicity Grading Scale for Healthy Adult and Adolescent Volunteers Enrolled in Preventive Vaccine Clinical Trials; tables for clinical abnormalities ([DHHS 2007](#)).

Unsolicited Adverse Events

All AEs spontaneously reported by the subject and/or in response to an open question from study staff or revealed by observation, physical examination or other diagnostic procedures must be recorded on the appropriate CRF. Unsolicited AEs of all severities will be reported from the time of study product administration through Day 30. After Day 30, only SAEs and AESIs will be reported through the end of the study (Day 180).

AE Severity

”Table 3: Solicited Adverse Reactions and Grading” will be used to assess and grade solicited AE severity. ”Appendix 3: Table of Laboratory Abnormalities” will be used to grade any laboratory abnormalities observed. If the adverse event is not covered in Table 3 and Appendix 3, the guidelines shown in Table 4 below should be used to grade severity. It should be pointed out that the term “severe” is a measure of intensity and that a severe AE is not necessarily serious.

Table 4. AE Severity Grading

Severity (Toxicity Grade)	Description
Mild (1)	These events do not interfere with the participant’s daily activities.
Moderate (2)	These events cause some interference with the participant’s daily activities and require limited or no medical intervention.
Severe (3)	These events prevent the participant’s daily activity and require intensive therapeutic intervention.

AE Relationship to Study Drug

The relationship of an AE to the study drug should be assessed using the following guidelines in Table 5.

Table 5. AE Relationship to Study Drug

Relationship to Drug	Comment
----------------------	---------

Definitely	Previously known toxicity of agent; or an event that follows a reasonable temporal sequence from administration of the drug; that follows a known or expected response pattern to the suspected drug; that is confirmed by stopping or reducing the dosage of the drug; and that is not explained by any other reasonable hypothesis.
Probably	An event that follows a reasonable temporal sequence from administration of the drug; that follows a known or expected response pattern to the suspected drug; that is confirmed by stopping or reducing the dosage of the drug; and that is unlikely to be explained by the known characteristics of the participant's clinical state or by other interventions.
Possibly	An event that follows a reasonable temporal sequence from administration of the drug; that follows a known or expected response pattern to that suspected drug; but that could readily have been produced by a number of other factors.
Unrelated	An event that can be determined with certainty to have no relationship to the study drug.

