8.4.3 Administration Instructions

Each dose will be administered via IM injection into the deltoid muscle on Day 1.

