12.3 Halting Criteria for Full Group (Cohorts 1 and 2)

The study will be paused if any of the following events occur in the full group (standard (n=18), mid (n=18) and high dose (n=18) groups) and enrollment may resume only after the DSMB reviews the events and permits the study to continue.

1. Any grade 4 (Table 3) solicited local or systemic reaction in the mid or high-dose groups considered to be at least possibly related to vaccination within 7 days after administration of the vaccine.
2. Three or more grade 3 (Table 3) solicited local or systemic reaction in the same dose group considered to be at least possibly related to vaccination that lasted at least 48 hours within 7 days after administration of the vaccine.
3. Any three participants with severe allergic reaction that is at least possibly related to vaccination within 24 hours after administration of the vaccine.
4. Any SAE within 28 days after administration of the vaccine considered to be at least possibly related to vaccination.
5. Any episode of myocarditis / pericarditis within 28 days after administration of the vaccine.
6. Any new episodes of elevated troponin, ECG and physical exam findings concerning for myocarditis / pericarditis within 28 days after administration of the vaccine.
7. Any death unless determined to be definitely not related to vaccination within 90 days after administration of the vaccine.

If the halting criteria is triggered for the high-dose group and further enrollment of this group is not recommended by the study investigators, DSMB or IRB, the study will continue randomized enrollment into the mid-dose and standard-dose groups with a 1:2 ratio to complete the enrollment of 60 participants total. Since the expected immunogenicity difference between these two groups will be smaller, we will require more participants to detect a difference between these two groups. The 1:2 enrollment ratio into the mid-dose and standard-dose groups will even the distribution of participants into these two groups. The primary endpoint analysis for safety and reactogenicity will not be affected by a restriction of participants into the mid-dose and standard-dose groups.

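### Table 5 has no causality rating for a new kind of event with plausible timing, although the SUSAR definition and halting criterion 4 both need one

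*Combined protocol and SAP*

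**What the plan says.** Section 11.1 makes Table 5 the reference for causality: "The relationship of an AE to the study drug should be assessed using the following guidelines in Table 5". Its four rows are:

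- **Definitely** has two routes. The row opens "Previously known toxicity of agent; or an event that follows a reasonable temporal sequence from administration of the drug", so a previously known toxicity qualifies alone. Any other event needs suitable timing, a recognised pattern, confirmation by stopping or reducing the drug, and no other reasonable explanation.
- **Probably** has one route. It needs timing, a recognised pattern, an event "that is confirmed by stopping or reducing the dosage of the drug", and little likelihood that the participant's condition or another treatment accounts for it.
- **Possibly** needs timing and an event "that follows a known or expected response pattern to that suspected drug", together with other factors that could readily have caused it.
- **Unrelated** is "An event that can be determined with certainty to have no relationship to the study drug".

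There is no row for unlikely or unassessable events, and no default.

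On exposure, Section 8.4.3 states: "Each dose will be administered via IM injection into the deltoid muscle on Day 1". Table 2 in Section 8.4.1 likewise gives Day 1 as the only administration in all three dose groups.

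On use of the rating, criterion 4 in both halting lists (Sections 12.2 and 12.3) reads "Any SAE within 28 days after administration of the vaccine considered to be at least possibly related to vaccination". Section 11.1 defines a suspected event by a reasonable possibility of causation. It defines a SUSAR as an event whose causal link is at least possible and which is not listed in the Investigator's Brochure or product labelling.

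**The concern.** A dose-finding study that goes up to 200 ug in a transplant population has to be able to register toxicities that nobody has described before. A rating scale that admits an event as possibly related only when it resembles something already known works against that purpose.

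The rating also drives action. Under criterion 4 it decides whether a serious event pauses enrolment for DSMB review. Section 5.3 ties required reporting of serious events to the IRB and FDA to judged relatedness. The trial is open-label and single-site, and the investigator is also the sponsor, so the dose is known to the person who assigns the rating. If the written scale gives that person no valid answer for a novel serious event, two careful assessors could handle the same event differently, and neither could be shown to have departed from the protocol.

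**Working it through.** No arithmetic applies. The check is whether the four rows cover every event that can follow one injection, and then which rules depend on the answer.

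**Step 1. Conditions in Table 5.**

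| Row | Timing | Recognised pattern | Stopping/reducing | Other explanations |
|---|---|---|---|---|
| Definitely, route 1 | previously known toxicity suffices | – | – | – |
| Definitely, route 2 | needed | needed | needed | none reasonable |
| Probably | needed | needed | needed | unlikely |
| Possibly | needed | needed | not needed | could readily explain it |
| Unrelated | – | – | – | certainty of no relationship |

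**Step 2. Apply the single Day 1 dose.** The stopping/reducing condition cannot be met. Probably is therefore out of reach, and Definitely survives only for previously known toxicities.

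**Step 3. Does that alter a decision?** The halting lists use one threshold, at least possibly related. The reporting rules in Sections 5.3 and 11.1 do not grade above it. The analyses in Sections 5.1, 14.3 and 14.5 summarise frequency, type, severity, laboratory extremes, onset, duration and outcome, with no breakdown by relationship. Only the label on the case report form is affected.

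**Step 4. Classify three kinds of event.**

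- *Recognised pattern, plausible timing:* Possibly is available where other causes exist, and Definitely where it is a previously known toxicity.
- *Known reaction, but worse or more frequent than expected:* Section 11.1 calls this unexpected, but the pattern is still known, so Possibly remains available.
- *New in nature, plausible timing, no certainty either way:* Definitely fails (not a known toxicity; route 2 needs a pattern and stopping/reducing). Probably fails on the same two conditions. Possibly fails on pattern. Unrelated fails on certainty. It fits 0 of 4 rows.

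**Step 5. Set the third kind beside Section 11.1.** A SUSAR must be both unlisted and at least possibly related. For an event new in nature, Table 5 withholds exactly the rating that the definition requires. The two cannot both be applied literally.

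**Step 6. Trace the halting criteria (same order in both lists).**

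- Criteria 1 and 2 concern solicited Table 3 reactions, which Section 11.1 describes as anticipated. They can be rated.
- Criterion 3 concerns severe allergic reactions. Section 1.2 already reports hypersensitivity with this vaccine, so these can largely be rated.
- Criterion 4 covers any serious event within 28 days that is at least possibly related. A novel type has no row.
- Criteria 5 and 6 (myocarditis/pericarditis and suggestive findings) carry no relatedness condition.
- Criterion 7 (death) applies unless the death is definitely not related, so it operates by default.

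What remains is a non-fatal serious event of a new kind under criterion 4. As an illustration, take hospitalisation for acute rejection two weeks after 200 ug. Rejection is not in Table 3, not among the Appendix 2 terms (a list that says it is not comprehensive), and not among the vaccine reactions described in Sections 1.2 and 2.1. Assuming the Investigator's Brochure does not list it, no row in Table 5 applies.

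**The case against.** The best defence is that Table 5 is offered as guidance, that the halting criteria never cite it, and that Section 11.1 plainly expects novel events to be ratable as possibly related. Since Unrelated demands certainty, the table does not permit such an event to be dismissed. Serious events go to the IRB whatever their cause (Sections 11.2.1 and 15.9), and the DSMB must approve each step after a sentinel group and before the high-dose group opens.

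These points limit the harm but do not remove the conflict. Judgement without a stated fallback gives inconsistent ratings. IRB reporting does not pause enrolment under criterion 4. DSMB approval at set steps is not the event-driven review that criterion 4 is meant to trigger.

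Three stronger readings are tempting and are not supported:

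- A reader might infer that the primary safety analysis would be distorted because relatedness tables collapse into one category. Relationship is recorded (Sections 9.1.6 and 11.1), but no analysis by relationship is planned.
- A reader might count criteria 1 to 4 and conclude that most of the halting list is compromised. Criteria 1 to 3 mostly concern known reaction patterns.
- A reader might conclude that every unexpected event lacks a category. Those unexpected only in severity or frequency can still be rated Possibly.

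**Conclusion.** The inconsistency is real and narrow. It is a conflict between stated rules, not a missing detail, and it matters because a safety pause can turn on it. The stopping-or-reducing clause does not suit a single-injection study but is inconsequential in itself. The gap between Possibly and Unrelated is what needs correcting.

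The documents give no basis for estimating how often such an event would occur, so no frequency is attached. The conclusion assumes that Table 5 is applied as written and that the event is not covered by the Investigator's Brochure, which is not among the documents. Section 11.4 (Medical Monitoring) is listed in the contents, but its text was not available here. If it sets out a causality review with a default rating, the practical exposure would be smaller, though Table 5 and the SUSAR definition would still disagree.

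**What to change.** 1. In Table 5, delete the stopping-or-reducing clause from Definitely and Probably.
2. Remove the recognised-pattern condition from Possibly, so that the row agrees with the reasonable-possibility and SUSAR language in Section 11.1.
3. Check the result for completeness. Possibly would still require that other factors could readily explain the event, so a novel event with no alternative cause would still fit no row unless that clause is also made non-mandatory. Events with doubtful timing that are not certainly unrelated also need a stated place.
4. Reconcile Table 5, Section 11.1 and the phrase at least possibly related in Sections 12.2 and 12.3, so that every event has one rating. Correct the cross-reference in Section 11.1 that points to Tables 3 and 4 for relationship, which is in Table 5.

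The halting rule should be left to the sponsor and the DSMB. They should see the revised table before it is adopted, because its wording affects when criterion 4 is met. In particular, if every event not certainly unrelated counted as Possibly, then any serious event within 28 days that could not be ruled out with certainty would pause the study. That is a change in practice and should be made deliberately or not at all.

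The cost is a table edit, some more events rated possibly related, and possibly more pauses for DSMB review.

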11.2 Serious Adverse Experiences (SAE)

An SAE is defined as any AE occurring at any dose that results in any of the following outcomes:

1. death
2. a life-threatening adverse experience
3. inpatient hospitalization or prolongation of existing hospitalization
4. a persistent or significant disability/incapacity
5. a congenital anomaly/birth defect

Other important medical events may also be considered an SAE when, based on appropriate medical judgment, they jeopardize the participant or require intervention to prevent one of the outcomes listed.

Participants will be instructed to call a study team line (attended 24-hours per day) if they experience any grade 4 symptom from the "Solicited Adverse Reactions and Grading" table (Table 3), any severe unsolicited AE (Table 4), or any SAE. The study team member will interview, document and triage the participant for further evaluation.

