10.2 Visit 1 Day 1 (Clinic): Booster Vaccine Day

1. For participants who meet inclusion/exclusion criteria, the investigator team will again review the study with the participant (or participant's legal representative) in person and obtain written informed consent and HIPAA authorization.
2. Record demographic data.
3. Record medical history.
4. Review of birth control history with female participants of childbearing potential (<1 year since start of menopause).

5. For women of childbearing potential, counsel participants to use adequate birth control methods required during the trial to avoid pregnancy.
6. For women of childbearing potential, urine pregnancy test will be checked prior to study drug administration on Visit 1 (Day 1).
7. Confirmation participants meet all inclusion criteria and no exclusion criteria review.
8. Review pre-study concomitant medications and therapies and record on the appropriate CRF.
9. Review of influenza and any all 2019-CoV vaccinations or other experimental coronavirus vaccines.
10. Vital signs (HR, BP, temperature, oximetry), and height and weight for determination of BMI.
11. Full physical exam will include assessments of the following organs and organ systems: skin, head, ears, eyes, nose, and throat (HEENT), neck, lungs, heart, liver, spleen, abdomen, extremities, lymph nodes (axillary and cervical), and nervous system.
12. Obtain blood samples for baseline: Total immunoglobulins (IgG, IgA, IgM), anti-RBD, anti-spike binding and neutralizing antibody levels, PBMCs collected for cellular response assays including flow cytometry with intracellular staining, whole blood collected for cellular response assays, troponin / CK and cytokines for storage.
13. Confirm group assignment: standard-dose, mid-dose or high-dose group.
14. Inform participants of their designated dose.
15. Administration of booster vaccine.
16. Participants will be observed for 30-minutes post injection administration.
17. Dispense daily diary of symptoms for first 7 days after injection dispensed to participant measuring FDA Toxicity Grading Scale and adverse events.

10.3 Visit 2 Day 3 +/-1 Day (Phone – 2 days post booster):

1. All participants will complete a daily diary of solicited and unsolicited AEs from the vaccination until 7 days post-vaccination. Reactogenicity will be measured by the occurrence of solicited injection site and systemic reactions for the first 7 days post-vaccination utilizing the FDA Toxicity Grading Scale.

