2. Participants will be contacted by telephone to query for safety events and review daily diaries. Based on the information collected, participants may be asked to return to the clinic for evaluation for an unscheduled visit.
3. Review daily diaries, AEs (solicited and unsolicited), SAEs, AESIs and MAAEs.
4. Participants will contact their primary care doctor, lung transplant pulmonologist or study principal investigator with any SAEs, AESIs or MAAEs.

10.4 Visit 3 Day 7 +/-2 Days (Clinic Visit – 6 days post booster):

1. Vital signs (HR, BP, temperature, oximetry), and height and weight for determination of BMI.
2. Symptom-directed (targeted) physical exam. Targeted physical examinations should also include an assessment for signs suggestive of AEs and AESIs. Interim or unscheduled physical examinations will be performed at the discretion of the PI or appropriate sub-investigator, if necessary, to evaluate AEs or abnormal clinical laboratory test results.
3. Obtain blood samples for follow-up: Total immunoglobulins (IgG, IgA, IgM), anti-RBD, anti-spike binding and neutralizing antibody levels, PBMCs collected for cellular response assays including flow cytometry with intracellular staining, whole blood collected for cellular response assays, troponin / CK and cytokines for storage.

5. Review daily diaries, AEs (solicited and unsolicited), SAEs, AESIs and MAAEs.

10.5 Visit 4 Day 30 +/- 7 Days (Clinic – 29 days post booster):

1. Vital signs (HR, BP, temperature, oximetry), and height and weight for determination of BMI.
2. Symptom-directed (targeted) physical exam. Targeted physical examinations should also include an assessment for signs suggestive of AEs and AESIs. Interim or unscheduled physical examinations will be performed at the discretion of the PI or appropriate sub-investigator, if necessary, to evaluate AEs or abnormal clinical laboratory test results.
3. Obtain blood samples for follow-up: Total immunoglobulins (IgG, IgA, IgM), anti-RBD, anti-spike binding and neutralizing antibody levels, PBMCs collected for cellular response assays including flow cytometry with intracellular staining, whole blood collected for cellular response assays, troponin / CK and cytokines for storage.
4. Review daily diaries, AEs (solicited and unsolicited), SAEs, AESIs and MAAEs.

10.6 Visit 5 Day 90 +/- 7 Days (Phone – 89 days post booster):

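### In Cohorts 1 and 2, no visible instruction asks participants to report a home-managed grade 3 solicited reaction between scheduled contacts, although halting item 2 counts such reactions once they last 48 hours.

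*Combined protocol and SAP*

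**What the plan says.** **Halting rule.** Section 12.3, item 2, pauses the study on "Three or more grade 3 (Table 3) solicited local or systemic reaction in the same dose group". Each reaction must be judged at least possibly related and must last 48 hours or more within 7 days of the dose. No other item in section 12.3 names grade 3 solicited reactions.

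**When participants are told to make contact.** Three visible instructions apply:
- Section 11.2: "Participants will be instructed to call a study team line (attended 24-hours per day) if they experience any grade 4 symptom". The same sentence adds severe unsolicited AEs and SAEs.
- The diary note under Table 3 in section 11.1: any grade 4 symptom, or "any other severe symptoms that prevents your daily activity AND requires you to see a doctor".
- Section 10.3, item 4: "Participants will contact their primary care doctor, lung transplant pulmonologist or study principal investigator with any SAEs, AESIs or MAAEs". Section 11.1 defines an MAAE by a hospitalization, an emergency room visit or another unscheduled encounter with medical personnel.

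**Scheduled contacts.** Section 10.3 sets "Visit 2 Day 3 +/-1 Day" as a phone call. Visit 3 is in clinic on Day 7, plus or minus 2 days (section 10.4). After that comes "Visit 4 Day 30 +/- 7 Days" (section 10.5). Appendix 1 marks diary review at Visits 2 and 3.

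**Follow-up of known events.** Section 11.1 states that "AEs will be followed to resolution or stabilization". It also has study clinicians follow reactogenicity symptoms that persist beyond 7 days.

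**Dosing pace.** Section 4.1 holds enrollment for 7 days after each sentinel pair. It states no spacing between doses within the two 27-participant cohorts.

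**The concern.** A pausing rule protects the participants who have not yet been dosed, so it works only as fast as the events it counts reach the study team. Here the rule counts a grade 3 solicited reaction, but the prompts to call start at grade 4 or at a need for medical care. Table 3 lets several reactions reach grade 3 with neither. For fatigue, myalgia and arthralgia the definition is "Significant; prevents daily activity", and for fever it is a temperature of 39.0 to 40.0 C.

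If such a reaction is the third to qualify in a dose group, more participants can be dosed after the threshold has been met and before anyone has judged relatedness or paused enrollment. Reactogenicity is a primary objective, and this is the only halting item in section 12.3 directed at grade 3 solicited reactions.

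**Working it through.** The plan gives no figure for this delay, so there is nothing to reproduce. The check has two parts: comparing the lists, and timing arithmetic.

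**1. Which grade 3 reactions escape the call-in lists?**
- Grade 3 chills require medical intervention by definition, and grade 3 nausea/vomiting is described as needing outpatient IV fluids. Both involve medical care, so the diary note and the MAAE instruction already cover them.
- Fatigue, myalgia, arthralgia and fever can reach grade 3 with no medical contact. They are not grade 4, not unsolicited and not MAAEs, and they need not be SAEs or AESIs. No visible list covers them.

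**2. Which onset times are affected?**
- Onset on the dosing day: the reaction is at about 48 hours at the nominal Day 3 call, 2 days after the dose, and is picked up there.
- Onset later but before the call: it is reported at the call, and the follow-up duty in section 11.1 then applies, although no 48-hour check is timed.
- Onset after the call: no contact is scheduled until Visit 3.
- Last onset that can qualify: 7 days after Day 1 is Day 8, and 8 - 2 = Day 6.

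**3. How long can a qualifying reaction go unseen?** Let C be the call day (2 to 4), V the day of Visit 3 (5 to 9) and t the onset day, with t after C and before V. The reaction qualifies at t + 2, so

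lag = max(0, V - (t + 2)).

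The worst case is onset just after the call (t = C):
- Nominal, C = 3 and V = 7: 7 - 5 = 2 days.
- Early call and late visit, C = 2 and V = 9: 9 - 4 = 5 days.
- C = 3 with V = 5, or C = 4 with V = 5 or 6: 0 days.

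Mean at nominal visits, assuming qualifying onsets uniform over Days 3 to 6: the lag is 5 - t for t from 3 to 5 and zero from 5 to 6. The area is 2 × 2 / 2 = 2, and 2 / 3 is about 0.67 day.

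**4. Early Visit 3.** With V = 5, onset between Day 5 and Day 6 can still qualify, at Day 7 to Day 8. The next scheduled contact is Visit 4, on Day 23 to 37. With V = 6, only onset at the Day 6 limit itself could qualify, so in practice there is no onset interval left.

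**5. Scale, under an assumed pace of enrollment.** The documents give no accrual rate. The Synopsis allows up to 12 months in total, with 6 months of follow-up and up to 7 months per participant. That leaves 5 to 6 months (21.74 to 26.09 weeks). If enrollment were even, 60 / 26.09 = 2.30 and 60 / 21.74 = 2.76 participants per week. Further participants dosed = rate × lag / 7:

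| Lag | Participants dosed meanwhile |
|---|---|
| 2/3 day | 0.22 to 0.26 |
| 2 days | 0.66 to 0.79 |
| 5 days | 1.64 to 1.97 |

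By the 2:1 allocation, about two thirds of these would receive the higher dose. Enrollment within a cohort could run faster, because sentinel holds and DSMB reviews use part of the time.

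**The case against.** The plan monitors reactogenicity by diary review at the Day 3 call and Visit 3, and keeps the 24-hour line for urgent triage. Any plan that reviews diaries at scheduled contacts carries some lag, and here it is at most 2 days at nominal visits. The dose level has already passed its sentinel pair and DSMB approval, and grade 4 reactions and related SAEs pause the study through other items. Calls about every grade 3 reaction would include some that resolve before 48 hours. All of this stands, and it is why the point is minor. It does not explain why a reaction the halting rule counts is left off call-in lists the plan already has.

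Section 11.4 (Medical Monitoring) is in the table of contents but not in the available text, and the DSMB charter is not provided. Either might describe closer review. That is a fair caveat, but it would not change the wording participants are given in the diary note or the call-in rule in section 11.2.

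A reader might infer more than the documents support:
- **That these reactions are lost to the count.** With Visit 3 at its nominal time or later, diary review should find them. They are delayed, not lost.
- **That detection can slip by weeks, with many participants dosed meanwhile.** Onset just after a Day 5 visit qualifies on Day 7, and Visit 4 on Day 23 to 37 would be 16 to 30 days later. This needs Visit 3 at the earliest edge of its window, a one-day band of onset, and no action under the section 11.1 duty to follow symptoms unresolved at 7 days. The documents do not say how often onset falls that late, so no dose count belongs with this case.
- **That the sentinel groups are exposed.** Enrollment at that dose level is held for 7 days and needs DSMB approval.

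**Conclusion.** The mismatch is real and minor; correcting it is a cheap improvement. In Cohorts 1 and 2, a home-managed grade 3 solicited reaction that starts after the Day 3 call can meet the 48-hour criterion 0 to 2 days before the team sees it at nominal visits. The mean is about 2/3 day if qualifying onsets are uniform over Days 3 to 6, and the lag reaches 5 days with a Day 2 call and a Day 9 visit. The case of a Day 5 visit followed by onset within the next day is a rare addition, and its delay cannot be sized from the documents.

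The consequence is conditional. Two qualifying reactions must already exist in the dose group, the third must start after the call, and it must prompt no medical contact. The conclusion also assumes that participants follow the written instructions without volunteering more, and that section 11.4 and the DSMB charter do not already close the gap.

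**What to change.** Add any grade 3 Table 3 reaction to the reasons to call the 24-hour line in section 11.2, and to the diary note under Table 3. Leave the halting thresholds in sections 12.2 and 12.3 as they are. Optionally, state in section 10.3 that a reported grade 3 reaction is followed by a contact 48 hours after onset, so that the duration criterion is checked when it falls due.

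The cost is one phrase in each of two places, plus one optional line. The line is already staffed. The downside is a few more calls, some about reactions that settle before 48 hours.
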